## **11 SAFETY ANALYSIS**

The safety and tolerability of AKB-9778 will be determined by incidence and severity of treatment emergent AEs and changes from baseline in ECG, vital sign measurements, clinical laboratory assay results (blood chemistry, hematology, fecal occult blood, and urinalysis), BCVA, IOP, slit lamp examinations, funduscopic examinations and FA. Continuous and qualitative variables will be summarized indicating change from baseline and shift tables, where appropriate. Some data will be summarized through treatment period as

well as throughout the study (treatment period plus follow-up period). Also, individual subject safety data will be listed.

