4.4 Potential Benefits and Risks

4.4.1 Potential Benefits and Risks of AKB-9778

Please see the AKB-9778 Investigator Brochure for additional discussion and information for the following section.

Collectively, the nonclinical pharmacology data in diverse models is consistent with the proposed mechanism whereby AKB-9778 inhibits VE-PTP resulting in Tie2 activation and improves endothelial function and vascular stabilization, supporting the potential efficacy of VE-PTP inhibition with AKB-9778 in a broad range of retinal pathology. The completed clinical Phase 2a study in subjects with DME shows that Tie-2 activation via AKB-9778 enhances treatment of macular edema when combined with an anti-VEGF inhibitor and has evidence of efficacy as monotherapy in the treatment of NPDR.

The safety of VE-PTP inhibition with AKB-9778 has been explored in nonclinical safety studies, in multiple nonclinical pharmacology studies and in seven clinical studies.

Clinically, AKB-9778 has shown no evidence of significant safety issues to date. A transient, generally asymptomatic reduction in blood pressure is observed reflecting the vasodilatory pharmacodynamic effect of Tie-2 activation. At doses above the 15 mg dose used in the Phase 1b AKB-9778-CI-2002 study, vasovagal events (presyncope/syncope) have been observed following the first dose of AKB-9778. A vasovagal event was observed after the first dose in 1/144 (0.7%) subjects in the Phase 2 AKB-9778-CI-2003 study. This subject did not experience any such events during the subsequent 3 months of dosing. No other vasovagal events were observed in this study. In both studies there was a significant correlation between baseline BP and change in BP. Specifically, subjects with higher BP had greater reductions in BP.

Based on nonclinical studies and clinical studies conducted to date, identified risks include transient injection site reactions, hepatotoxicity, hemodynamic effects, hematologic and plasma lipid effects, and vascular effects.

In the nonclinical rat studies, findings of reversible and acute, individual hepatocellular necrosis of minimal severity were observed that correlated with elevations in AST and ALT in some animals. In dogs, adverse liver findings have only been observed in the 28-day toxicity study, at the high dose, and included one incidence of mild randomly distributed foci of mild necrosis,

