11.6 Safety Analysis

All subjects who receive at least one dose of any study medication will be included in the safety analysis. All safety endpoints are listed in [Section 5.6.3](#).

All AEs reported during the study period will be recorded and coded using MedDRA terminology. An AE will be considered as treatment-emergent if it has an onset during the treatment period or is pre-existing and worsens after the first dose of study medication is administered. The incidence of all reported treatment-emergent adverse events (TEAEs) will be summarized using system organ class and preferred term by treatment group and overall, using counts and percentages. Separate analyses will be performed for ocular and non-ocular TEAEs. These summaries will also be provided for treatment related TEAEs and TEAEs by severity. For ocular TEAEs, the subject will be considered to have had the TEAE if at least one eye had the TEAE.

Continuous safety endpoints collected at each visit will be summarized with number of subjects, mean, standard deviation (SD), median, minimum, and maximum for each treatment group and for all subjects. Qualitative variables collected at each visit will be summarized using counts and percentages for each treatment group and for all subjects. Summaries will also include change from baseline and shift tables, where appropriate. Individual subject safety data will be listed.

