### 5.5 Safety Endpoints

Safety endpoints include:

- Incidence and severity of systemic and ocular AEs
- Ocular AEs at Study eyes, all qualified eyes and unqualified fellow eyes during treatment period.
- Shift from baseline in body system assessments for the parameters general appearance, HEENT (Head, Ears, Eyes, Nose and Throat), cardiovascular, respiratory, abdomen/gastrointestinal, musculoskeletal, and dermatologic at week 12, 24, 36, 48.
- Change from baseline in vital sign measurements (SBP, DBP, HR, BMI, Weight and Temperature) at every 4 weeks.
- Change from baseline in ECG parameters (HR, PR, QRS and QTcF) at week 24, 48.
- Change from baseline in clinical laboratory assay results (blood chemistry (at every 4 weeks), hematology (at every 8 weeks), fecal occult blood test (at week 24, 36, 48), and urinalysis (at week 24, 36, 48).
- Mean change from baseline in ETDRS Best Corrected Visual Acuity (BCVA) letter score in the study eyes, all qualified eyes and unqualified fellow eyes at every 4 weeks.
- Proportion of subjects with a loss of ≥15 letters, loss of ≥10 letters and loss of ≥5 letters in BCVA compared to baseline at week 48.
- Mean change from baseline in Spectral Domain Optical Coherence Tomography (SD OCT): Central Subfield Thickness (CST) in the study eyes, all qualified eyes and unqualified fellow eyes at week 12, 24, 36, 48.

- Proportion of subjects with increase of  $\geq 100$   $\mu\text{m}$  and increase of  $\geq 50$   $\mu\text{m}$  SD OCT: CST in the study eyes, all qualified eyes and unqualified fellow eyes at week 48.
- Change from baseline in Intraocular Pressure (IOP), with additional sub-group analysis with baseline IOP  $< 16$  mmHg and baseline IOP  $\geq 16$  mmHg in the study eyes and fellow eyes at week 12, 24, 36, 48.
- Shift from baseline in Slit Lamp Biomicroscopy examination for the parameters Eyelids, Cornea, Conjunctiva, Anterior Chamber, Iris/Pupil and Lens in all qualified eyes and unqualified fellow eyes at week 12, 24, 36, 48.
- Shift from baseline in Dilated Indirect Ophthalmoscopy examination for the parameters Vitreous, Macula, Optic Nerve, and Peripheral Retina in all qualified eyes and unqualified fellow eyes at week 12, 24, 36 and 48.

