## **10.2 Secondary, Exploratory and Exploratory Sub-Study Efficacy Endpoint Analysis**

Secondary efficacy endpoints are summarized in Section 5.2, and involve alternative analyses of DRSS results, showing the proportion of patients who develop sight-threatening complications of DR (DME & PDR). Measures of kidney function (UACR and eGFR) are exploratory efficacy endpoints. Exploratory sub-study endpoints are derived from OCT-Angiography, Ultra-wide field fluorescein angiography, Ultra-wide field color photographs, and electroretinography. Details of these variables and their analysis are contained in separate SAPs.

Normality assumption will be tested for any endpoint of continuous nature. If normality assumption is violated, appropriate transformation and/or non-parametric analysis will be employed. Otherwise, all secondary, exploratory and exploratory sub-study endpoints of continuous nature will be analyzed using ANCOVA model, and all inferential analyses will use a 2-sided 5% significance level. For the exploratory efficacy endpoints UACR and eGFR, for internal decision-making purposes, a 1-sided 10% significance level will be used. Whenever possible, a mixed model repeated measures (MMRM) model will be utilized to analyze this data. The model will include change from baseline as the dependent variable. The p-value and 95% CI from the model is baseline parameter adjusted.

For MMRM, visit will be treated as the repeated variable within a subject. Within-subject error, an unstructured variance-covariance will be applied; in case of non-convergence, compound symmetry will be used. MMRM model for UACR and eGFR is adjusted by the baseline HbA1c, Baseline Systolic BP, log-transformed Baseline UACR, and ACEi/ARB use.

Secondary, exploratory and exploratory sub-study endpoints of a dichotomous nature will be analyzed using the same approach as outlined for the primary efficacy endpoint.

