### **11.1.2 Electrocardiogram (ECG)**

Change from baseline for ECG parameters will be presented along with their associated 95% confidence intervals. Potentially clinically significant findings will also be presented based on the following categories:

- The proportion of patients obtaining treatment-emergent absolute QTcF values  $> 450$  ms and  $\leq 480$  ms;  $> 480$  ms and  $\leq 500$  ms; and  $> 500$  ms.
- The proportion of patients obtaining a QTcF increase from baseline values  $> 30$  and  $\leq 60$  ms; and  $> 60$  ms.
- The proportion of patients obtaining a QRS change from baseline  $> 25\%$  resulting in QRS  $> 120$  ms
- The proportion of patients obtaining a PR interval change from baseline  $> 25\%$  reaching a value  $> 220$  ms
- The proportion of patients obtaining a heart rate change from baseline  $> 25\%$  decrease resulting in a heart rate  $< 50$  beats per minute (bpm) and heart rate change from baseline  $> 25\%$  increase resulting in a heart rate  $> 100$  bpm

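### Blood pressure change is summarised per arm with no baseline adjustment, placebo-corrected difference or confidence interval, although the protocol links it to baseline pressure and to an identified risk

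*SAP*

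**What the plan says.** **Endpoint and method.** SAP section 5.5 lists "Change from baseline in vital sign measurements (SBP, DBP, HR, BMI, Weight and Temperature) at every 4 weeks". SAP section 11 sets the method: "Continuous and qualitative variables will be summarized indicating change from baseline and shift tables, where appropriate". Protocol section 11.6 agrees: "Continuous safety endpoints collected at each visit will be summarized with number of subjects, mean, standard deviation (SD), median, minimum, and maximum", by arm and overall, with change and shift tables added where suitable. None of these sections names an arm contrast, a confidence interval or a covariate for blood pressure.

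**What is known about the effect.** Protocol section 4.4.1 states that "identified risks include transient injection site reactions, hepatotoxicity, hemodynamic effects, hematologic and plasma lipid effects, and vascular effects". On the two studies just discussed there it adds: "In both studies there was a significant correlation between baseline BP and change in BP. Specifically, subjects with higher BP had greater reductions in BP".

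**What the SAP does elsewhere.** Section 10.2 models continuous efficacy endpoints by ANCOVA or MMRM, where "The p-value and 95% CI from the model is baseline parameter adjusted". Baseline systolic pressure is already a covariate there for UACR and eGFR. For the ECG, which includes heart rate, section 11.1.2 says "Change from baseline for ECG parameters will be presented along with their associated 95% confidence intervals" and adds threshold categories for heart rate.

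**Design.** Randomisation is stratified by screening DRSS alone (Protocol section 8.3.2, SAP section 3.2). Sitting pressure and heart rate are also measured 30 and 90 minutes after the dose on Day 1 and at Month 6 (Protocol sections 9.3.2.3 and 9.3.2.10, Appendix A). SAP section 5.5 does not name these readings. SAP Table 1 runs from baseline (Day 1 or earlier) straight to the Week 4 window (Days 15 to 42), so the Day 1 post-dose values have no analysis slot.

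**The concern.** The protocol identifies baseline pressure as a predictor of pressure change, and the safety analysis leaves it out. Screening systolic pressure may lie anywhere from 100 to just under 180 mmHg (Protocol section 7.2.2), and nothing in the design balances it between arms. An arm that starts higher by chance will tend to show a larger fall, and one that starts lower can mask part of a real fall.

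The arms will be compared even though no test is planned. SAP section 11 uses vital-sign change to judge safety and tolerability, and Protocol section 4.3 reports the earlier Phase 2 study in terms of differences between groups. What is at stake is how precisely and how clearly the trial describes a known effect of the drug.

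**Working it through.** **The plan's own figure.** The documents give no figure for blood pressure. Their one power statement is for the primary endpoint: more than 85% with 45 evaluable per arm, 30% against 5%. Full enumeration of the two-sided Fisher test gives 86.3%, and 45 / (1 − 0.10) = 50 per arm. Both reproduce, and neither is affected by this point.

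**Inputs.** From the plan: n = 50 per arm. Assumed, because the documents are silent: systolic SD 15 mmHg (range 10 to 20), the same before and after; correlation r between baseline and follow-up 0.5 (range 0.3 to 0.9).

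**Formulas for the difference between two arms.**
- SD of the chance baseline imbalance: SD × √(2/n)
- Shift in the raw-change difference, given an imbalance d: −(1 − r) × d
- Variance, raw change: (2/n) × SD² × 2(1 − r)
- Variance, baseline-adjusted: (2/n) × SD² × (1 − r²)
- Proportional cut in variance: 1 − (1 + r)/2, which depends on neither SD nor n

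**At SD 15, r = 0.5, n = 50.**
- Imbalance SD: 15 × √(2/50) = 3.0 mmHg. A 1-SD imbalance shifts the raw difference by 0.5 × 3.0 = 1.5 mmHg; a 1.96-SD imbalance shifts it by 2.9 mmHg.
- SE, raw change: 15 × √1 × 0.2 = 3.00 mmHg; 95% half-width 5.88.
- SE, adjusted: 15 × √0.75 × 0.2 = 2.60 mmHg; 95% half-width 5.09.
- Cut in variance: 1 − 1.5/2 = 25%.

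**Across r, at SD 15 and n = 50.**

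| r | half-width, raw (mmHg) | half-width, adjusted (mmHg) | cut in variance | shift from a 1-SD imbalance (mmHg) |
|---|---|---|---|---|
| 0.3 | 6.96 | 5.61 | 35% | 2.10 |
| 0.5 | 5.88 | 5.09 | 25% | 1.50 |
| 0.7 | 4.55 | 4.20 | 15% | 0.90 |
| 0.8 | 3.72 | 3.53 | 10% | 0.60 |
| 0.9 | 2.63 | 2.56 | 5% | 0.30 |

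**Other inputs.** For SD 10 to 20 the imbalance SD runs from 2.0 to 4.0 mmHg. At r = 0.5 the half-width then goes from 3.92 to 3.39 mmHg (SD 10) or from 7.84 to 6.79 (SD 20). With 45 per arm and SD 15 it goes from 6.20 to 5.37.

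**Simulation check.** In 20,000 simulated trials with no drug effect (SD 15, r = 0.5, n = 50), both estimators averaged about zero. The raw difference had slope −0.50 on the baseline imbalance and the adjusted one about 0. The variance ratio was 1.33, as the formula 2/(1 + r) predicts.

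**The case against.** **Safety is descriptive by design.** No blood pressure hypothesis is planned, and raw change in a randomised trial is unbiased. This stands. A reader might infer that the planned summary is biased or invalid. It is neither: the shift is conditional on the imbalance that happens to occur.

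**An imbalance would be visible.** Protocol section 11.3 includes vital signs among the baseline summaries, and n, mean and SD per arm allow an unadjusted difference and its SE to be worked out by hand. This is partly right, although the baseline list in SAP section 9.1 does not name blood pressure. Seeing an imbalance does not correct for it, and the reader would still have to build the interval.

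**The gain may be small.** Same-day readings could correlate strongly, and at r = 0.8 to 0.9 the variance falls by only 10% to 5%. This stands. The protocol gives no coefficient, one of the two earlier studies was open-label with dose cohorts (Protocol section 4.3), and regression to the mean alone would produce some correlation. Adjustment deals with regression to the mean as well.

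**The 4-weekly visits are the wrong place to look.** Protocol section 4.3 describes effects that are transient and follow the plasma curve. In the 3-month study they were seen after Day 1 dosing, with no group difference in pressure or heart rate at the end of treatment. This stands, and it shapes the fix: a model limited to monthly visits would miss the readings where an effect is most likely.

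**Heart rate and other safety measures.** A reader might extend the point to heart rate, QTcF, BCVA and IOP. The documents do not support this. The reported correlation, "In both studies there was a significant correlation between baseline BP and change in BP", concerns blood pressure, and ECG heart rate already has an interval and threshold categories. No baseline dependence is reported for the other three, and SAP section 5.5 already splits IOP by baseline value.

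**Conclusion.** The point holds for systolic and diastolic pressure, as an improvement in precision and interpretability. The plan gives no placebo-corrected estimate with an error bar for a documented haemodynamic effect, and it omits a baseline covariate that its own background section shows to be related to the outcome.

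The size rests on an assumed r. The variance reduction is material at r of 0.5 or below (25% or more) and slight at 0.8 to 0.9. The mmHg figures also rest on the assumed SD and on equal variance before and after. The missing contrast and interval do not depend on r.

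A reader might also infer a threat to the trial's main conclusion or to the detection of symptomatic events. Neither follows. The primary analysis and sample size are untouched, and symptomatic events are still captured as adverse events and through the separate safety reviews.

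**What to change.** In SAP section 11.1, add a supportive baseline-adjusted analysis of change in systolic and diastolic pressure, following the approach of SAP section 10.2:

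- **4-weekly visits:** MMRM with treatment, visit, treatment by visit and the Day 1 pre-dose value as covariate, or ANCOVA at each visit.
- **Post-dose readings:** ANCOVA at 30 and at 90 minutes on Day 1 and at Month 6, with the same covariate. The Month 6 pre-dose value is measured after randomisation and should not replace it. Name these readings in SAP section 5.5 and give them their own analysis time points.
- **Report:** each active arm minus placebo with a 95% CI, with no multiplicity claim.
- **Keep** the descriptive tables. Vital-sign heart rate may be included for completeness. No change is needed for QTcF, BCVA or IOP.

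The dosing sections do not say whether the once-daily arm's active syringe is the morning or the evening one. The post-dose contrast for that arm should be read with that known.

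The cost is a paragraph of SAP text and a few tables built on a model the SAP already uses. No new data are needed. The downside is a few more safety intervals to interpret, none of them adjusted for multiplicity.

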## **11.1 Safety Endpoint Analysis**

### **11.1.1 Adverse Events**

All AEs reported during the study and follow-up period will be recorded and coded using MedDRA version 20.1 terminology. An AE will be considered as treatment-emergent if it has an onset during the treatment period or is pre-existing and worsens after the first dose of study medication is administered. When the date of AE is same as date of randomization, the site will be queried to ensure timing of AE start relative to first dose is determined.

The incidence of all reported treatment-emergent adverse events (TEAEs) will be summarized using system organ class and preferred term by treatment group and overall, using counts and percentages. All adverse events will also be presented by relationship and severity. Further, serious adverse events and adverse events leading to discontinuation will also be presented.

Separate analyses will be performed for ocular and non-ocular TEAEs. For ocular TEAEs, the subject will be considered to have had the TEAE if at least one eye had the TEAE. Ocular TEAEs will be summarized separately for all eyes, study eyes, all qualified eyes (study eyes and qualified fellow eyes) and unqualified fellow eyes.

Subjects may have more than one AE per system organ class and preferred term. At each level of subject summarization, a subject will be counted once if they reported 1 or more events and will be reported with the highest severity. In cases where severity or relationship is missing, the most conservative approach will be taken (i.e. highest severity and assumed to be related).

A listing of TEAEs will be generated showing adverse event location (OD, OS or non-ocular), duration of TEAEs with onset date, severity, relationship with study medication and change in status of ongoing event. Also, listing for serious adverse events, and adverse events leading to discontinuation will be generated.

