9 STUDY PROCEDURES AND SCHEDULE OF ACTIVITIES

Please see [Appendix A](#) for a detailed table of the Schedule of Activities.

A one-month duration in this study is defined as 4 weeks/28 days. The 12-month Treatment period is 48-weeks/336 days.

This study includes the following periods and visits:

- Screening visit (up to 28 days prior to Baseline)
- Baseline visit (pre-dosing period on Day 1)
- Treatment Period (Days 1 through Month 12 (Week 48)); including:
 - Investigative site visits on Day 1, Day 7 (phone-call), and monthly (i.e., every 4 weeks) thereafter until the Month 12 (Week 48) EOT visit
 - Homecare nurse visits on Screening and Months 3, 6, 9, 12 (EOT)
- Follow-Up Period 1 Month (4 weeks) Post-Treatment

The following sections describe the procedures to be completed during the study. Subjects are to be assessed by the same Investigator or site personnel whenever possible.

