9.3 Schedule of Activities

The Schedule of Activities is presented in [Appendix A](#) and shows the timing of planned study procedures to be conducted at the study site and at the home care nursing visits. Every effort should be made to adhere to the procedure schedule and all assessments should be completed at each study visit.

The Screening, Baseline, Treatment, and Follow-up Periods will require subject participation for approximately 56 weeks.

Study procedures, clinical assessments (including laboratory assays), and PK, biomarker and genetic sampling will be performed as indicated in the Schedule of Activities.

Subjects will be responsible for self-administration of study medication which is provided in prefilled sterile syringes. The subject will self-inject BID on a morning and evening schedule as detailed in [Section 8.3.5](#). Subjects will dose BID with the exception of Day 1 when the subject will dose the first (AM) dose at the clinic and will begin the BID dosing schedule on Day 2. No PM dose will be taken on Day 1.

At the visit on Day 1, the site will train the subject on SC study medication administration and dosing diary completion. After the pre-dose activities have been completed, the subject will self-administer the AM dose of study medication.

After the subject has completed the EOT visit, no further subcutaneous dosing will occur.

Study visits on Day 1, Month 6 and Month 12 EOT should be scheduled for the morning. The remainder of the site visits should also be scheduled for the morning when possible. Subjects will maintain a daily study medication diary and will record timing and location of dose.

At the site visits on Day 1 and Months 1 through 11, subjects will be dispensed subcutaneous study medication and dosing supplies.

Subjects discontinuing study medication sooner than the planned 12-month dosing period or withdrawing from the study should complete the Month 12 EOT assessments including the EOT assessments at the EOT site visit (See [Section 9.3.2.16](#)) and the EOT homecare nurse visit (See [Section 9.3.3.5](#)).

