9.3.1 Visit Windows

Plasma PK samples collected at 30 and 90 minutes after dosing of study medication on Day 1 and Month 6 should be collected within ± 10 minutes of the target time. If for any reason, the sampling time point for a given sample falls outside of the visit window, the sample must still be collected. For all samples; the exact time of sample collection will be recorded.

Blood pressure and heart rate evaluations performed must be conducted within ± 20 minutes of the designated time.

Subjects will only use AM syringes for dose administration in the morning and PM syringes for dose administration in the evening. Subjects should administer their daily doses around the same time every morning and evening, if possible. If a dose is missed, this dose should be skipped and the subject should maintain the morning and evening dosing schedule.

The Day 7 phone call must be conducted within ± 3 days.

Site visits scheduled for Months 1 through 12 should be conducted within 28 days times the study month number ± 3 days relative to the baseline visit (e.g. Month 1 visit window is 28 ± 3 days from Day 1, Month 2 visit window is 56 ± 3 days from Day 1, etc.).

Homecare nurse visits scheduled for Screening, Months 3, 6, 9 and 12 should be conducted within 1 week after the corresponding site visit. The Follow-up homecare visit occurs 4 weeks ± 3 days after the EOT visit at the site.

The fecal occult blood specimen collection and shipping to the Central Laboratory should be conducted by the subject within the week following the corresponding site visit.

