18 APPENDICES

18.1 Appendix A: Schedule of Activities

Protocol Activities	Schedule of Activities [A]														F/U EOT + 1M		
	Screening		Baseline		Treatment Period [B]												
	Day		Month														
	Day - 28 to Day - 1	Day 1 Pre-Dose	Day 1	Day 7	M1	M2	M3	M4	M5	M6	M7	M8	M9	M10	M11		
Informed Consent	X																
Eligibility Criteria	X																
Demographics	X																
Medical/Ophthalmic History	X	X														X	
Height Weight and Temperature [C]	X											X				X	
Body System Assessments [D]	X						X				X		X		X	X	
ECG [E]	X										X					X	
Vitals [F]																	
Sitting BP and HR	X	X	X		X	X	X	X	X	X	X	X	X	X	X	X	
Eye and Vision Exams																	
ETDRS BCVA	X	X			X	X	X	X	X	X	X	X	X	X	X	X	
Slit Lamp Biomicroscopy	X	X					X			X			X			X	
Intraocular Pressure	X	X					X			X			X			X	
Dilated Indirect Ophthalmoscopy	X	X					X			X			X			X	
SD OCT	X						X			X			X			X	
Fundus Photography[G]	X						X			X			X			X	
Fluorescein Angiography [H]	X									X						X	
OCT Angiography Sub Study [I]		X					X			X			X			X	
ERG Sub Study [I]		X					X			X			X			X	
Laboratory Procedures																	
Serum/Urine Pregnancy [J]	X	X								X						X	
Hematology[K]	X	X				X		X		X		X		X		X	
Chemistry [L]	X	X			X	X	X	X	X	X	X	X	X	X	X	X	
Urinalysis [M]		X								X			X			X	
Fecal Occult Blood Test [N]	X									X			X			X	
Biomarker Blood Sampling		X														X	
Blood sampling for Genetic Analyses		X															
PK Blood Sampling [O]			X								X						
Dosing [P]				X	X	X	X	X	X	X	X	X	X	X	X	X	
Study medication dispensing & return, diary review [Q]				X		X	X	X	X	X	X	X	X	X	X	X	
AE collection [R] [S]	X	X	X	X	X	X	X	X	X	X	X	X	X	X	X	X	
Concomitant Medication Review [T]	X	X	X	X	X	X	X	X	X	X	X	X	X	X	X	X	

[A] Assessments are conducted at the study site unless otherwise noted.

[B] Site visits scheduled for Months 1 through 12 should be conducted within 28 days times the study month number ± 3 days relative to the baseline visit. Homecare nurse visits scheduled for Screening, Months 3, 6, 9 and 12 should be conducted within 1 week after the corresponding site visit. The Follow-up homecare nurse visit is to be conducted 4 weeks (± 3 days) after the EOT visit at the investigative site.

[C] Height is collected at screening only.

[D] Body system assessments are conducted at the home care nursing visit.

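### The two clauses of the treatment-emergent definition have different end dates: new events in the 4-week follow-up fall outside the TEAE tables, while worsening events in the same weeks fall inside

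*SAP*

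**What the plan says.** **Definition.** SAP 11.1.1: "An AE will be considered as treatment-emergent if it has an onset during the treatment period or is pre-existing and worsens" once the first dose has been given. Protocol 11.6 opens the same way, "An AE will be considered as treatment-emergent if it has an onset during the treatment period", with the same worsening clause. Neither gives a number of days after the last dose.

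**Treatment period.** Protocol section 9 describes it as "Treatment Period (Days 1 through Month 12 (Week 48)); including" site and homecare visits, and adds "The 12-month Treatment period is 48-weeks/336 days". The 4-week Follow-Up Period is a separate item in the same list. SAP section 11 also treats follow-up as something added to the treatment period.

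**End of dosing and what comes after.** Protocol 9.3: "After the subject has completed the EOT visit, no further subcutaneous dosing will occur". Appendix A, note D: "Body system assessments are conducted at the home care nursing visit". Protocol 9.3.1: "Homecare nurse visits scheduled for Screening, Months 3, 6, 9 and 12 should be conducted within 1 week after the corresponding site visit". Stool kits are handed out at the Month 12 site visit and used within the following week (protocol 9.2.2 and 9.3.2.16). The follow-up homecare visit is 4 weeks, plus or minus 3 days, after EOT. AE reporting runs from consent to the final required visit (protocol 10.3.1).

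**Reporting.** SAP section 11 bases the safety conclusion on treatment-emergent events together with changes from baseline. It says that some data will also be summarised over the whole study, without saying which.

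**The concern.** One rule gives two answers in the same week. A subject whose existing condition worsens two weeks after EOT has a TEAE. A subject with a new event on the same day does not. Neither document gives a reason for the difference.

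The excluded weeks are few, but they contain a planned safety check. The follow-up homecare visit repeats the body-system assessment, including direct inspection of the skin. The protocol's background reports dermal nodules and gastrointestinal angiectasis in the nine-month dog study. It also says that it is not known whether ectasias will appear in patients dosed for longer than the three months studied so far. The end of a 48-week course is the longest exposure in the trial, so a clear rule for what counts there is worth having.

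A second weakness is that the end of the treatment period is not fixed relative to the last dose. This affects findings first detected at the Month 12 homecare skin check, at the Month 12 stool test, or at the EOT assessments of subjects who stopped early. Two programmers could classify the same record differently.

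**Working it through.** **1. Length of the treatment period.** Protocol section 9 sets a month at 28 days: 12 × 28 = 336 days, as stated. Participation is 4 + 48 + 4 = 56 weeks, also as stated.

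**2. Calendar around the end of dosing.** Protocol 9.3.1 says: "Site visits scheduled for Months 1 through 12 should be conducted within 28 days times the study month number ± 3 days" relative to baseline. With the first dose on Day 1:

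- EOT site visit: 1 + 336 ± 3 = Days 334 to 340, nominally Day 337. This matches the SAP's Week 48 target day.
- Month 12 homecare visit and stool collection: EOT to EOT + 7, nominally Days 337 to 344, at latest 340 + 7 = Day 347.
- Follow-up visit: EOT + 28 ± 3, nominally Day 365, range 334 + 25 = 359 to 340 + 31 = 371.

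**3. Where the treatment period could be taken to end.** The documents allow at least three readings:

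- Day 336, counting 336 days from Day 1.
- The EOT site visit, Days 334 to 340.
- The Month 12 homecare visit, up to Day 347. Protocol 9.3.3.5 heads this visit as part of the treatment period, and section 9 lists it there.

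For early stoppers no end is stated. Their EOT assessments come as soon as possible after medication is stopped (protocol 7.6).

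**4. Classification under the current wording.**

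| Event | Day 1 to EOT | Week after EOT | Rest of follow-up |
|---|---|---|---|
| New onset | TEAE | Depends on the reading in step 3 | Not a TEAE |
| Pre-existing, worsens | TEAE | TEAE | TEAE |

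**5. Size in time.** Nominal excluded time is 28 / (336 + 28) = 28/364 = 7.7%. Visit windows make it 25 to 31 days.

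**6. Size in planned checks.** Post-baseline body-system assessments fall at Months 3, 6, 9, 12 and follow-up. One of five (follow-up) is plainly outside the treatment period and one (Month 12) is ambiguous. Post-baseline stool tests fall at Months 6, 9 and 12. None of three is plainly outside and one is ambiguous.

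**7. Size in events.** The documents give no rate of new events in follow-up. Assume that a proportion p of 50 subjects per arm has one. The expected number is 50p, and the chance of at least one in an arm is 1 − (1 − p)^50.

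| Assumed p | Expected per arm | Chance of at least one |
|---|---|---|
| 1% | 0.5 | 39% |
| 2% | 1 | 64% |
| 5% | 2.5 | 92% |
| 10% | 5 | 99% |

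These are illustrations, not estimates.

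**8. Other routes into the tables.** The SAP's Week 48 window for body-system and stool data is Days 295 to 378. Month 12 results (latest Day 347) therefore enter the Week 48 by-visit tables. The follow-up visit (Days 359 to 371) also falls in that window, but SAP 3.3 prefers the matching scheduled visit, and SAP 5.5 specifies body-system shifts only at Weeks 12, 24, 36 and 48. So where the Month 12 check was done, a new finding at follow-up does not reach those shift tables.

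**The case against.** Much of the case on the other side stands.

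- **Labelling.** A reader might infer that the Month 12 skin check and stool test are excluded by definition because dosing has ended. The documents do not support that. The rule refers to the treatment period and not to the last dose, and the protocol lists the Month 12 homecare visit under that period.
- **Onset, not detection.** A nodule found after EOT but dated to the dosing weeks is a TEAE. The protocol gives a half-life of about 1 to 2 hours and says that the dog nodules resolved rapidly on withdrawal. Both make onset on treatment more plausible than new onset off drug.
- **Liver.** Month 12 chemistry is drawn at the EOT site visit itself. The later homecare visits include no liver test, so a liver argument applies at most to early stoppers.
- **No loss of data.** SAP 11.1.1 presents all AEs by relationship and severity, and gives SAEs and AEs leading to discontinuation separately. SAP sections 7 and 11 provide listings of subject data.
- **A legitimate choice.** An on-treatment definition is recognisable for a drug cleared this fast, and a wider window adds background events.

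The last point would justify ending both clauses at the end of treatment. It does not justify ending one and leaving the other open. Nor does any of these points say when the treatment period ends for an early stopper. The SAP's promise to summarise some data over the whole study does not name AE incidence.

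**Conclusion.** The concern holds as an inconsistency in a stated rule, with limited reach. New events in follow-up are outside the TEAE tables by system organ class and preferred term, the ocular and non-ocular TEAE analyses and the TEAE listing; worsening events in the same weeks are inside. The affected time is nominally 28 of 364 post-baseline days (7.7%). How many events would move, and whether any comparison between arms would change, cannot be determined from the documents.

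Findings first detected in the week after EOT, or at an early stopper's EOT assessments, are ambiguous. It would be wrong to say that the definition removes what the Month 12 checks are meant to find, or that safety data go unreported.

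This rests on reading the treatment period as protocol section 9 sets it out, with follow-up separate, and on taking at face value the SAP's statement that all AEs are presented by relationship and severity. The change is worth making because it is cheap, uses AEs already collected, and makes classification consistent in tables on which the safety conclusion relies.

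**What to change.** In SAP 11.1.1 and protocol 11.6, define a TEAE as any event with onset, or any pre-existing condition that worsens, from the first dose through the final protocol-required visit (the 4-week follow-up). Use the same end date for both clauses and the same rule for early stoppers, whose window runs to their own follow-up visit.

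Keep an on-treatment-only TEAE table as a supplement. For that table, state the last day that counts relative to the last dose, and how to date a finding first detected after EOT. If only the SAP is changed, record the departure in SAP 1.1, which at present lists none.

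The cost is a wording change in two places and one extra table; no new data collection is needed. The downside is that some background events occurring off drug will be counted in every arm. The supplementary table lets a reader see their effect.

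A narrower alternative is to end both clauses at a stated end of treatment. That would also remove the inconsistency, but new follow-up events would stay outside the TEAE tables.
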